3.3.1 Eligibility Criteria

3.3.1.1 Inclusion Criteria

Each patient must meet all of the following criteria to be eligible for enrollment in this study:

1. Patient has signed an ICF before any study-specific procedures are performed.

2. Patient is an ambulatory, community-dwelling male or nonpregnant female and is at least 18 years old at the Screening Visit. Lactating females must agree not to breastfeed.
3. Patient has a diagnosis of GERD and reports experiencing GERD symptoms (heartburn or regurgitation) on ≥ 4 days per week during the 8 weeks before the Screening Visit while taking standard QD PPI therapy.
4. Patient has been receiving individually optimized, standard-labeled dose, QD, PPI therapy (treatment that, according to the Investigator's judgment, could not be further improved by changing the brand or timing of PPI administration) for a minimum of 8 weeks before the Screening Visit. Patients should be on a PPI dose and schedule that is consistent with the approved labeling ([Appendix 11](#)). Patients who have their PPI modified during the Screening Period may be re-screened after 8 weeks of optimized, standard-labeled dose, QD, PPI therapy provided they have not previously entered the Pretreatment Period.
5. An EGD with approximately 48 to 96 hours of pH monitoring (with a Bravo device) during the Screening Period (while the patient continues taking their PPIs) demonstrates 1 or more of the following:
 - a. Erosive esophagitis (Grade A or greater based on the Los Angeles classification of esophagitis; [Appendix 5](#)) on EGD
 - b. Evidence of pathological acid reflux (pH is < 4 for $\geq 4.2\%$ of the recording time) during at least 1 of the 24-hour time intervals of pH testing with the Bravo device
6. Patient reports heartburn severity (HS, Item #1 on mRESQ-eD) ≥ 3 (moderate) on at least 2 days and has an average HS of ≥ 2 (mild) during the last 7 days before randomization.
7. Sexually active female patients of childbearing potential (i.e., women who are not postmenopausal or who have not had a bilateral oophorectomy, hysterectomy, or tubal ligation) must agree to use 1 of the following methods of birth control from the date they sign the ICF until 24 hours after their final dose of study drug:
 - a. Hormonal contraception (i.e., contraceptive implant or injectable hormonal contraceptive)

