 - b. Double-barrier birth control (e.g., condom plus intrauterine device, diaphragm plus spermicide, etc.) Patients may continue taking oral contraceptives while using one or more barrier methods.
 - c. Maintenance of a monogamous relationship with a male partner who has been surgically sterilized by vasectomy
8. Females of childbearing potential must have a negative serum pregnancy test at the Screening Visit and a negative urine pregnancy test at the Randomization Visit prior to dosing.

9. Patient agrees not to make any changes to their usual diet during the study, except those patients participating in Bilitec testing, who must agree to a “white diet” during Bilitec testing only.
10. Patient is compliant with eDiary completion; that is, they have adequately completed the eDiary questions on at least 5 days each week during the 14 calendar days before the start of the Treatment Period.
11. Patient is compliant with QD PPI dosing during the 14 calendar days before the start of the Treatment Period. Patients are considered compliant if, as reported in the eDiary, they take their PPI on at least 5 days each week.
12. Patient is fluent and literate in English or Spanish.
13. Patient is able to operate the eDiary adequately and agrees to adhere to the study requirements.
14. For patients who are receiving supplementation of a fat-soluble vitamin in order to correct or avoid a fat-soluble vitamin deficiency, the patient is willing to take the vitamin supplement at least 4 hours before taking study medication.

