5.10 EFFICACY ANALYSIS

Unless otherwise specified, efficacy analyses will be based on both the mITT and the PP Populations.

Baseline values for efficacy parameters will be derived from the eDiary and/or electronic clinical report form (eCRF) data collected for the last week of the Pretreatment Period (or Week -1), specifically the period from 7 days prior to the day of randomization up to the time of randomization. If data for Week -1 is not available, data for Week -2 (the second last week of the Pretreatment Period) will be used.

For continuous efficacy parameters, the analysis value for an analysis period is defined as the average of the non-missing values during that period.

For weekly responder parameters based on daily eDiary assessments, a patient who missed 4 or more daily assessments during an analysis week will not be considered a responder for that week.

[Table 5.10-1](#) provides the analysis time windows allowed for efficacy analyses based on daily assessments and [Table 5.10-2](#) provides the analysis time windows allowed for efficacy analyses based on weekly assessments.

Table 5.10-1. Analysis Time Windows for Efficacy Analysis – Daily Assessments

Period	Analysis Week	Begins ^a	Ends ^a
Pretreatment (Baseline ^b)	Week -2	Day -14	Day -8
	Week -1	Day -7	Day -1 (Day before randomization) ^c
Treatment	Week 1	Day 1 (Day of Randomization) ^d	Day 7
	Week 2	Day 8	Day 14
	Week 3	Day 15	Day 21
	Week 4	Day 22	Day 28
	Week 5	Day 29	Day 35
	Week 6	Day 36	Day 42
	Week 7	Day 43	Day 49
	Week 8	Day 50	Day 56
	Week 9	Day 57	Day 63
	***	***	***

- a. Relative to the date of randomization (Day 1).
- b. Baseline values for efficacy parameters will be derived from the daily eDiary collected in the Pretreatment Period Week -1 (Week -2 if data from Week -1 not available)
- c. Day 1 for efficacy parameters derived from the morning diary.
- d. Day 2 for efficacy parameters derived from the morning diary.

Table 5.10-2. Analysis Time Windows for Efficacy Analysis – Weekly Assessments

Period	Analysis Week	Begins ^a	Ends ^a
Pretreatment (Baseline ^b)	Week -2	Day -11	Day -5
	Week -1	Day -4	Day -1 (Day before randomization)
Treatment	Week 1	Day 7	Day 10
	Week 2	Day 11	Day 17
	Week 3	Day 18	Day 24
	Week 4	Day 25	Day 31
	Week 5	Day 32	Day 38
	Week 6	Day 39	Day 45
	Week 7	Day 46	Day 52
	Week 8	Day 53	Day 59
	Week 9	Day 60	Day 66

a. Relative to the date of randomization (Day 1).

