5.10.3 Other Efficacy Parameters

Other efficacy parameters include the following:

1. Percent change from baseline to Week 8 in weekly regurgitation frequency score (WRFS) in patients with a baseline WRFS of ≥ 2 (sometimes)

The WRFS for an analysis week is defined as the average of available daily regurgitation frequency scores (DRFS) during that week. DRFS is defined as the maximum of the 2 items measuring regurgitation (Regurgitation [liquid or food moving upwards toward your throat or mouth] and An acid or bitter taste in the mouth) from a particular day collected with the mRESQ-eD instrument.

2. Percent change from baseline to Week 4 in WRFS in patients with a baseline WRFS of 2 (sometimes)

3. Change from baseline to Week 8 in WRFS

4. Change from baseline to Week 4 in WRFS

5. Proportion of patients who are overall regurgitation responders (of patients with a baseline WRFS of ≥ 2 [sometimes])

An overall regurgitation responder is a patient who is a weekly regurgitation responder for at least 4 of the 8 treatment weeks and for at least 1 of the final 2 treatment weeks (i.e., Week 7 and Week 8). A weekly regurgitation responder is a patient with a decrease of $\geq 30\%$ from baseline in WRFS.

6. Proportion of patients with a DRFS of no more than rarely (≤ 1) on any day during Week 8

7. Proportion of patients with a DRFS of no more than rarely (≤ 1) on any day during Week 4

8. Change from baseline to Week 8 in the number of days per week where DRFS was no more than rarely (≤ 1)

9. Change from baseline to Week 4 in the number of days per week where DRFS was no more than rarely (≤ 1)

10. Change from baseline to Week 8 in the weekly average of each of the daily symptom assessments

11. Weekly means for daily sleep assessments (number of awakenings, hours of sleep, sleep quality)

12. Weekly means for weekly symptom bothersomeness assessments, symptom relief assessments, and treatment satisfaction assessment

For analysis of continuous parameters (#1, 2, 3, 4, 8, 9, 10, 11, and 12), summary statistics will be presented by treatment group. Each IW-3718 group will be compared with the placebo group using an ANCOVA model with treatment group and esophagitis status as fixed-effect terms and

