the corresponding baseline efficacy parameter value as a covariate. Note that for parameters without a baseline value (e.g., Treatment Satisfaction), an ANOVA model (in lieu of ANCOVA) will be used with treatment group and esophagitis status as fixed-effect terms.

For analysis of responder parameters (#5, 6, and 7), the counts and proportion of responders will be calculated for each treatment group. The proportions of responders between each IW-3718 group and the placebo group will be compared using a CMH test controlling for esophagitis status.

Corresponding to efficacy parameters 8 and 9, additional analyses will be provided for the following parameters: 8a. Change from baseline to the 8-week Treatment Period in proportion of days where DRFS was no more than rarely (≤ 1); 9a. Change from baseline to the first 4 weeks of Treatment Period in proportion of days where DRFS was no more than rarely (≤ 1).

Change/percent change from baseline in WHSS, WRFS, and the weekly average of each of the individual daily symptom assessment items (GERD & dyspepsia) will be summarized/analyzed by week, and the LS mean changes/LS mean percent changes will be plotted across treatment weeks.

The proportion of Degree of Relief responders (reported a score of 1-Significantly Relieved or 2-Moderately Relieved on the Degree of Relief question for at least 4 of the 8 treatment weeks) will be summarized by treatment group for heartburn, regurgitation, and overall GERD symptoms.

In addition, the GSRS-self will be summarized by treatment group by visit for each of the 15 items and for each of the 5 domains: abdominal pain (3 items), reflux symptoms (2 items), indigestion (4 items), diarrhea (3 items), and constipation (3 items). The EOT Visit difficulty of swallowing question will also be summarized by presenting the count and proportion of patients in each of the 4 categories (from Not at all Difficult to Extremely Difficult) by treatment group.

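### Read literally, SAP 5.10.3 plans by-week percent change for WRFS and all 14 daily symptom items with no baseline restriction, although WRFS and 13 of the items can start at or near 0

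*SAP*

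**What the plan says.** After its numbered parameters, SAP 5.10.3 adds a set of by-week analyses. They cover "Change/percent change from baseline in WHSS, WRFS, and the weekly average of each of the individual daily symptom assessment items (GERD & dyspepsia" items, to be summarized or analyzed each week, and "LS mean changes/LS mean percent changes will be plotted across treatment weeks". The sentence states no minimum baseline.

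The surrounding text bears on this as follows.

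- **Scales.** SAP 4.1.1.1 lists six severity items scored 0-5, four frequency items scored 0-4 and four dyspepsia items scored 0-10. On each scale 0 means the symptom was absent.
- **Baseline.** It comes from Week -1, with Week -2 as fallback. For continuous parameters, "the analysis value for an analysis period is defined as the average of the non-missing values during that period" (SAP 5.10).
- **Entry.** Protocol 3.3.1.1 sets a symptom floor on one diary item only. Criterion 6 begins "Patient reports heartburn severity (HS, Item #1 on mRESQ-eD" and requires a mean of at least 2 over the last 7 days. Criterion 3 needs only that the patient "reports experiencing GERD symptoms (heartburn or regurgitation) on" at least 4 days a week, so regurgitation is not required.
- **Listed WRFS parameter.** SAP 5.10.3 #1 is "Percent change from baseline to Week 8 in weekly regurgitation frequency score (WRFS) in patients with a baseline WRFS of" at least 2. Protocol 3.7.4.2 #1 has the same floor.
- **Listed item parameters.** These are absolute changes only: SAP 5.10.2 #9, and SAP 5.10.3 #10, "Change from baseline to Week 8 in the weekly average of each of the daily symptom assessments". Section 6 of the SAP does not list item-level percent change as a departure from the protocol.
- **Zero baselines.** The SAP text gives no rule. Section 5.1.2 says only that missing data are not imputed unless stated otherwise.

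**The concern.** Percent change divides by the baseline. For a symptom the patient did not have in Week -1 it does not exist, and for one the patient barely had it is dominated by the denominator. Improvement stops at -100%, while worsening can run to several hundred percent or more. An ANCOVA of such values gives LS means that a few patients can move, and patients with a zero baseline drop out of that item's analysis with no rule saying so.

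The plan recognizes the problem for its listed Week 8 WRFS percent change and guards against it with the floor of 2, but the by-week sentence does not repeat the floor. As written, the by-week WRFS percent-change plot and the listed parameter would describe different patients. What is at stake is the readability and precision of supportive displays for WRFS and for symptoms such as cough, hoarseness, nausea and difficulty swallowing.

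**Working it through.** **The plan's own figure.** SAP 5.13 gives 58 per arm, difference 0.70, SD 1.35 and two-sided alpha 0.05. Pairwise: 0.70 / (1.35 x sqrt(2/58)) = 0.70 / 0.2507 = 2.79, and 2.79 - 1.96 = 0.83, so power is 79.7% against the stated 80%. Linear contrast (-3, -1, 1, 3) on effects 0, 0.385, 0.385, 0.77: 2.31 / (1.35 x sqrt(20/58)) = 2.31 / 0.793 = 2.91, so power is 83.0%, consistent with at least 80%. The point does not depend on these figures. They supply the 58 per arm used below and show that the sizing concerns heartburn only.

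**Which measures have a floor.** Items: 6 + 4 + 4 = 14. Heartburn item 1 has a baseline mean of at least 2 by criterion 6. DHSS is the daily maximum of three items including item 1, so baseline WHSS is at least the item 1 mean, hence at least 2. That leaves 14 - 1 = 13 items without a floor, plus WRFS.

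**Smallest non-zero baseline.** Eligibility requires that "they have adequately completed the eDiary questions on at least 5 days each week", so a Week -1 mean rests on 5 to 7 scores. A single score of 1 gives 1/7 to 1/5.

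**Percent change = 100 x (w - b) / b**, where w is the weekly mean and b the baseline.

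| Baseline b | One-point rise, 100/b | Rise to 1.0, 100(1 - b)/b |
|---|---|---|
| 2 | +50% | not applicable |
| 1 | +100% | 0% |
| 1/5 | +500% | +400% |
| 1/7 | +700% | +600% |
| 0 | undefined | undefined |

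The largest possible increase from b = 1/7 is +2700% on the 0-4 scale, +3400% on 0-5 and +6900% on 0-10. With a floor of 2 the limits are +100%, +150% and +400%. One patient going from 1/7 to 1 shifts the mean of a 58-patient arm by 600/58 = about 10 percentage points.

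**Illustration on assumed data.** The documents do not give the distribution of item baselines, so every input here except the arm size is an assumption.

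- Four arms of 58; a 0-5 item; 7 diary days a week; ANCOVA on arm, a random binary stratum and item baseline; zero baselines dropped for percent change only.
- Ordinary patients: person mean N(2.6, 0.7) clipped to 0.8-4.5, daily SD 0.8, scores rounded and clipped to 0-5. On treatment the person mean is multiplied by N(0.70, 0.30) clipped to 0-1.6, and by a further 0.78 in the active arm compared with placebo.
- Near-absent patients, share s: each day scores 1 with a patient-specific probability drawn from Beta(1, 1/q - 1), mean q = 0.15 or 0.30, otherwise 0; the probability is multiplied by 0.78 in that active arm.

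Results for the LS mean difference, with s from 10% to 30%:

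| | s = 0 | Tendency persists within patient | Tendency redrawn at each period |
|---|---|---|---|
| SE, percent change (points) | 6.0 | 7.1 to 9.5 | 7.4 to 13.1 |
| Power, percent change | 72% | about 60% to 37% | 54% to 25% |
| Power, absolute change | 74% | about 70% to 62% | 69% to 59% |

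Between 2.5% and 13.4% of patients have no percent-change value. In the redrawn setting the mean difference is -15.2 points at s = 0 and between -14.8 and -17.3 at s = 10% to 30%, so the loss is mainly one of precision.

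**The case against.** The strongest reply is that the sentence is shorthand. It uses slashes twice, follows the numbered parameters and can be read as displaying those parameters by week, with percent change where applicable. On that reading the WRFS floor carries over and the items get absolute change only. This cannot be excluded, so a reader who infers that the sponsor has definitely committed to unrestricted percent change goes further than the text proves. But the SAP does not say 'as applicable', and it names WRFS and every item in the same phrase as percent change.

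Other replies have partial force.

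- SAP 5.1.1 calls for n, median, minimum and maximum, so small samples and skew would be visible in the summaries. That does not repair the LS mean comparisons or the plots.
- SAP section 1 places table and figure specifications in a separate document, not available here, which may contain a zero-baseline rule. It should not be inferred that no rule exists anywhere, only that the SAP text has none.
- The trial is exploratory, p-values are nominal and nothing is powered on single items, so power serves here only to compare two ways of analysing the same data. This stands and limits the importance of the point.
- The upper end of the illustration (SE about 13, power about 25%) requires that a nearly symptom-free patient's tendency at baseline says nothing about later weeks. Persistence within a patient is at least as plausible and gives the smaller loss. The direction is the same under both.

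**Conclusion.** The point holds as a minor one: a cheap improvement to an ambiguous sentence. Taken literally, it yields undefined or extreme values for WRFS and for 13 of the 14 items, and it omits the floor that the plan itself sets for its listed WRFS percent change. The arithmetic on scales and entry criteria needs no assumption. The loss in this trial cannot be stated, because the frequency of low baselines is not given. On the assumed data the SE rises from about 6 to about 7 to 9.5 points with a persistent tendency, up to about 13 without it, and percent change loses clearly more power than absolute change.

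Two stronger readings are tempting and not supported. One is that the primary result is at risk: the primary endpoint, WHSS generally and heartburn item 1 are protected by the entry floor. The other is that treatment comparisons would be systematically biased: low baselines are fixed before randomization, so the harm is lost precision and chance imbalance.

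**What to change.** In the by-week sentence of SAP 5.10.3, limit percent change and its plots to WHSS, heartburn item 1, and WRFS in patients with baseline WRFS of at least 2. Report the other 13 items as absolute change with the item baseline as covariate, which SAP 5.10.2 #9 and 5.10.3 #10 already provide for. A stated zero-baseline rule with n reported per week would settle the undefined cases but leave the extreme values just above 0.

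The cost is one sentence before unblinding and fewer outputs. The downside is that those 13 items no longer appear on a percent scale. Optionally, SAP 5.10.5 could note that its WRFS percent change is parameter #1 of 5.10.3 with its floor; the fix does not depend on that.

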5.10.4 Exploratory Analyses

The following analyses intend to explore the relationship between measures of bile acid, acid reflux, and clinical response.

- a. Sensitivity and specificity of bile acid levels measured in saliva as a test for bile acid pathophysiology with Bilitec test findings as the reference standard
- b. Correlation between Bilitec test findings and Bravo pH monitoring results
- c. Bilitec test findings as a predictor of response to treatment
- d. Bile acid levels in saliva as a predictor of response to treatment
- e. Bravo pH monitoring results as a predictor of response to treatment

Analyses (a) and (b) will be conducted based on the Screened Population; all other analyses will be conducted using the mITT Population.

5.10.5 Subgroup Analyses

Subgroup Analyses of efficacy parameters will be based on the mITT Population.

Esophagitis Status

Subgroup analysis by esophagitis status (erosive esophagitis vs. no erosive esophagitis at screening) will be performed for the following efficacy parameters.

- Percent change from baseline to Week 8 in WHSS
- Overall Heartburn Responder
- Percent change from baseline to Week 8 in WRFS
- Overall Regurgitation Responder
- Percent change from baseline to Week 8 in saliva bile acid level

Baseline WHSS

Subgroup analysis by baseline WHSS (≤ 3 vs. >3) will be performed for the following efficacy parameters.

- Percent change from baseline to Week 8 in WHSS
- Overall Heartburn Responder

Baseline WRFS

Subgroup analysis by baseline WRFS (≤ 3 vs. >3) will be performed for the following efficacy parameters.

- Percent change from baseline to Week 8 in WRFS
- Overall Regurgitation Responder

Baseline Bile Acid Level in Saliva

Subgroup analysis by baseline bile acid level in saliva (positive vs. negative) will be performed for the following efficacy parameters.

- Percent change from baseline to Week 8 in WHSS
- Overall Heartburn Responder
- Percent change from baseline to Week 8 in WRFS
- Overall Regurgitation Responder

Bilitec Monitoring Status

Subgroup analysis by Bilitec monitoring status (performed vs. not performed at screening) will be performed for the following efficacy parameters.

- Percent change from baseline to Week 8 in WHSS
- Overall Heartburn Responder
- Percent change from baseline to Week 8 in WRFS
- Overall Regurgitation Responder

Bilitec Bile Acid Status

Subgroup analysis by Bilitec bile acid status (positive vs. negative at screening) will be performed for the following efficacy parameters.

- Percent change from baseline to Week 8 in WHSS
- Percent change from baseline to Week 8 in WRFS

5.10.6 Rescue Medicine Use

Patients will report the frequency of their nighttime use of rescue medicine (liquid antacid) in the morning diary and their daytime use of rescue medicine in the evening diary. Nighttime use, daytime use, and overall daily use of rescue medicine will be summarized by treatment group for each treatment week and for the Treatment Period.

5.11 HEALTH OUTCOMES ANALYSIS

5.11.1 SF-12V2 Health Survey

Change from baseline to Week 4 and Week 8 in SF-12V2 (both LOCF and OC) will be summarized by treatment group for each of the 8 health concepts (physical functioning, role limitations due to physical health problems, bodily pain, general health, vitality [energy/fatigue], social functioning, role limitations due to emotional problems, and mental health [psychological distress and psychological well-being]) and for each of the two summary measures (the physical component and mental component).

5.11.2 EQ-5D-3L

Change from baseline to Week 4 and Week 8 in EQ-5D-3L (both LOCF and OC) will be summarized by treatment group for each of the 5 questions assessing the following domains: mobility, self-care, usual activities, pain/discomfort, and anxiety/depression. Change from baseline to Week 4 and Week 8 in heath state as assessed by a 0 to 100 visual analogue scale (both LOCF and OC) will also be summarized by treatment group.

5.12 SAFETY ANALYSIS

Safety analyses will be performed using the Safety Population. Safety data summaries will be presented for each treatment group as well as for IW-3718 overall.

For analysis of safety parameters, the last non-missing value before the first dose of double-blind study drug will be used as baseline.

[Table 5.12-1](#) below presents the visits assigned for the safety analysis corresponding to the range of trial days (window) during which an actual visit may have occurred.

Table 5.12-1. Visit Time Windows for Safety Analysis

Derived Visit	Scheduled Test / Visit Day^a	Window
Baseline	Day 1	Days \leq 1
Day 15 Visit	Day 15	Days [2, 22]
Day 29 Visit	Day 29	Days [23, 43]
Day 57 Visit	Day 57	Days \geq 44
End of Treatment ^b	Final or termination visit	

a. Relative to the date of randomization; Day 1 = the day of randomization.

b. “End of Treatment” will be presented in analysis tables for safety parameters, including clinical laboratory and vital signs.

Test/Visit Day will be calculated as follows: test/visit date – date of randomization.

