3. STUDY DESIGN

ICP-3718-202 is a multicenter, randomized, double-blind, placebo-controlled, parallel-group, 8-week study, consisting of 3 distinct periods as illustrated in [Figure 3.0-1](#) below. The study will enroll patients who have GERD and continue to experience GERD symptoms while receiving QD, standard-dose PPI therapy that in the investigator's opinion has been optimized. Eligible patients will continue to take their PPI and will be randomized to placebo, 500 mg IW-3718 twice daily (BID), 1000 mg IW-3718 BID, or 1500 mg IW-3718 BID.

Figure 3.0-1. Overview of Study Design

Note: There is no Day 0

* This visit represents the end of the study

Screening Period: The Screening Period starts with the signature of the informed consent form (ICF) and may last for up to 28 days. During this period, patient eligibility for entry into the Pretreatment Period will be determined.

Pretreatment Period: The Pretreatment Period is defined as the 14 to 21 calendar days immediately before the Randomization Visit. During this period, patients will be required to use a handheld electronic diary (eDiary) to complete daily assessments (GERD symptoms, dyspepsia symptoms, assessment of sleep, and use of per-protocol rescue medicine) for at least 5 days each week during the last 14 calendar days before the Randomization Visit and weekly assessments

(symptom bothersomeness and degree of relief questions) at least once during the last 7 calendar days before the Randomization Visit in order to be eligible for randomization.

Treatment Period: The Treatment Period begins with treatment assignment and lasts for 8 weeks. Patients will be stratified by whether they have, or do not have, erosive esophagitis on the screening esophagogastroduodenoscopy (EGD) and randomly assigned to 1 of 4 treatments (1:1:1:1) within each stratum: placebo, 500 mg IW-3718 BID, 1000 mg IW-3718 BID, or 1500 mg IW-3718 BID. During this period, patients will continue to use the eDiary to provide their daily assessments (GERD symptoms, dyspepsia symptoms, assessment of sleep, and use of per-protocol rescue medicine) and weekly assessments (symptom bothersomeness, degree of relief, and treatment satisfaction questions).

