5.6 MEASUREMENT OF TREATMENT COMPLIANCE

The first dose of study medication will be taken in clinic at the Randomization Visit (Day 1). Patients should take their second dose that evening immediately upon completion of dinner. During the Treatment Period, patients will take study medication BID at home, in the morning (immediately upon completion of breakfast) and in the evening (immediately upon completion of dinner), even on study visit days. The last dose of study medication will be taken the morning of the EOT Visit. The double-dummy dosing requires all patients to take three tablets for each dose.

Dosing compliance for the Treatment Period is defined as the number of tablets taken by a patient during the Treatment Period divided by the number of tablets that were expected to be taken during the Treatment Period multiplied by 100. The total number of tablets taken will be calculated as total number of tablets dispensed minus total number of tablets returned minus total number of tablets lost. The total number of tablets expected to be taken during the Treatment Period is the number of days between the date of first dose taken and the date of last dose taken, inclusive, multiplied by 6 (multiplied by 6 minus 3 if the last dose is a morning dose). Patients will be included in the period summary only for the periods they were on study (i.e., the periods that are prior to or contain the last dose date).

Descriptive statistics for study drug compliance will be presented for the Safety Population by treatment group.

Patients will record their PPI administration each day (once daily) in their eDiary. PPI compliance for a specified period is defined as the number of days for which a patient answered Yes to the PPI administration question in the eDiary divided by the total number of days for which the patient provided an answer (Yes or No) to the PPI administration question in that period multiplied by 100. PPI compliance will be summarized by treatment group for the Safety Population.

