7. DATA HANDLING CONVENTIONS

7.1 REPEATED OR UNSCHEDULED ASSESSMENTS OF SAFETY PARAMETERS

If a patient has repeated assessments prior to the start of double-blind study drug, then the results from the final non-missing assessment made prior to the start of the double-blind study drug will be used as baseline. If end-of-study assessments are repeated or if unscheduled visits occur, the last non-missing post baseline assessment will be used as the end-of-study assessment for generating summary statistics. However, all post-baseline assessments will be used for PCS value determination as described above and all assessments will be presented in the data listings.

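### The SAP's safety visit-day formula runs one day behind its own Day 1 definition, which misplaces off-schedule assessments on Days 2, 23 and 44 in the by-visit safety summaries

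*SAP*

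**What the plan says.** Table 5.12-1 in SAP 5.12 assigns safety assessments to derived visits by study day: Baseline is day 1 or earlier, the Day 15 Visit is days 2 to 22, the Day 29 Visit is days 23 to 43, and the Day 57 Visit is day 44 or later. Footnote a fixes the scale: "Relative to the date of randomization; Day 1 = the day of randomization". The line under the footnotes gives the calculation: "Test/Visit Day will be calculated as follows: test/visit date – date of randomization". The note to the design figure in SAP section 3 adds: "There is no Day 0".

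Two other rules bear on the point.

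- **Baseline value.** SAP 5.12 says that "the last non-missing value before the first dose of double-blind study drug will be used as baseline", and SAP 7.1 repeats this for repeated assessments.
- **End of Treatment row.** Table 5.12-1 has a separate row for the final or termination visit, with no day window attached.

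**The concern.** The footnote and the formula cannot both be followed. A date minus itself is 0, so the formula gives the day of randomization a number that the study calendar does not contain, and it gives every later date a number one too low for the windows. Laboratory and vital sign values are summarized at each assessment time point (SAP 5.12.2 and 5.12.3), so the window decides which row a value enters. Two programmers who each follow a different line of the same section would produce different by-visit tables. At stake is the placement of assessments that fall next to a window boundary.

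**Working it through.** **Inputs.** The formula, footnote and windows come from SAP 5.12. The visit schedule comes from SAP Table 4.4-1: Week 2 at Day 15 ± 3, Week 4 at Day 29 ± 3, Week 8 at Day 57 + 3.

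**Notation.** Let k = assessment date − randomization date, which is the SAP formula. On a calendar with no Day 0, the true study day is d = k + 1 when k ≥ 0, and d = k when k < 0.

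**Step 1: the plan's own figure.** On the day of randomization k = 0, whereas footnote a requires 1. The stated Day 1 is not reproduced. The nominal visits on Days 15, 29 and 57 give k = 14, 28 and 56.

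**Step 2: which scale the windows use.** The two later cut-points are midpoints of the scheduled days on the Day 1 scale: (15 + 29)/2 = 22 and (29 + 57)/2 = 43. On a scale starting at 0 they would be (14 + 28)/2 = 21 and (28 + 56)/2 = 42. The windows therefore belong to the Day 1 scale, and the formula is the part that does not fit.

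**Step 3: the boundary days.**

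| True day d | Formula k = d − 1 | Window from formula | Window from true day |
|---|---|---|---|
| 2 | 1 | Baseline (≤ 1) | Day 15 (2 to 22) |
| 23 | 22 | Day 15 (2 to 22) | Day 29 (23 to 43) |
| 44 | 43 | Day 29 (23 to 43) | Day 57 (≥ 44) |

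Day 23 is 29 − 23 = 6 days from Day 29 but 23 − 15 = 8 days from Day 15. Day 44 is 57 − 44 = 13 days from Day 57 but 44 − 29 = 15 days from Day 29. In both cases the formula picks the more distant visit.

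**Step 4: all other days.** Both rules were applied to every date from 49 days before to 74 days after randomization. Only the three days in the table change window. Before randomization the two rules agree, since d = k.

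**Step 5: scheduled visits.**

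- Week 2, Days 12 to 18: k = 11 to 17, inside 2 to 22.
- Week 4, Days 26 to 32: k = 25 to 31, inside 23 to 43.
- Week 8, Days 57 to 60: k = 56 to 59, at or above 44. Protocol Table 2 prints this window as ± 3. Days 54 to 56 would give k = 53 to 55, also at or above 44.

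No scheduled visit within its permitted range moves.

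**Step 6: with the + 1 restored.** Randomization is Day 1, the nominal visits are Days 15, 29 and 57, and true Days 2, 23 and 44 fall in the Day 15, Day 29 and Day 57 windows.

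**The case against.** The strongest reply is that the intended convention is already plain and the consequences are slight. Footnote a sits beside the formula, the scheduled days match it, and the efficacy windows in SAP Table 5.10-1 use the same Day 1. On this view a + 1 was simply left out. That is probably how the error arose, but the calculation is an explicit instruction, and it is wrong as written.

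The reply is right about the limits, and two stronger readings should be set aside.

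- **A post-dose Day 2 value becomes the baseline.** A reader might infer this from the Baseline label. The documents do not support it. SAP 5.12 defines the baseline value by timing relative to the first dose, and SAP 7.1 says that "results from the final non-missing assessment made prior to the start of the double-blind study drug will be used as baseline". The first dose is taken in clinic on Day 1 (SAP 5.6), so a Day 2 value cannot qualify. Even the correct Baseline window covers the hours after dosing on Day 1, so it is the dosing rule, not the window, that separates pre-dose from post-dose values.
- **Early-termination data are generally misfiled.** Such an assessment can move in the by-visit summary if it falls on one of the three days. It still reaches the End of Treatment row, which has no day cut-offs.

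The reach is narrow in other ways too. Under SAP 7.1, all post-baseline assessments feed the determination of potentially clinically significant (PCS) values, and all assessments are listed. ECGs are summarized only at baseline and the end-of-treatment visit (SAP 5.12.4). Laboratory tests are not scheduled at Week 2. Safety analyses are descriptive (Protocol 3.7.5).

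**Conclusion.** The contradiction is real and minor. As written, the formula disagrees with footnote a and with the no-Day-0 convention, and it misassigns assessments on exactly three study days: 2, 23 and 44. Only off-schedule assessments (unscheduled, early-termination or out-of-window) can fall on those days, and only the by-visit descriptive safety summaries are affected. A Day 2 value gets the wrong label and drops out of the Day 15 summary. No efficacy, power or sample-size figure changes.

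This rests on three conditions.

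- The formula is applied literally. The table and listing specifications are in a separate document (SAP section 1), so the error is shown in the SAP text, not in any program.
- The displaced value would otherwise have been used in its correct visit row.
- Post-baseline status for PCS values is taken from the dosing date. If it were programmed from the window label, a Day 2 value could be missed there as well.

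The documents do not give the number of assessments on these days, so the number of affected records cannot be stated.

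**What to change.** Replace the line under Table 5.12-1 with a two-part definition:

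- for dates on or after randomization, day = test/visit date − date of randomization + 1;
- for earlier dates, day = test/visit date − date of randomization.

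Then confirm that the programming specification uses the same definition. The cost is one line of SAP text. The windows, footnotes, baseline rule and End of Treatment row stay as they are, and no clinical procedure is touched.
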